#### 5.4 Concomitant Medications

Whenever a concomitant medication or study agent is initiated or a dose changed, investigators must review the concomitant medication's and study agent's most recent product information sheet, Investigator's Brochure, or updated information from DAIDS to obtain the most current information on drug interactions, contraindications, and precautions.

Additional drug information may be found on the updated ACTG Drug Interactions Database located at: http://tprc.pharm.buffalo.edu/home/di search/.

# 5.4.1 Required Medications

See inclusion criteria (section 4.1) for specifications about ART. Participants must be on ART (not study provided) as specified in the inclusion criteria.

Discontinuation of ART regimen will result in permanent discontinuation of the study treatment. Participants may change ART regimens under the supervision of their physicians as long as they continue to meet all inclusion and exclusion criteria.

### 5.4.2 Prohibited Medications

The following medications/products are prohibited while participants are taking the study agents:

- Immunosuppressives (eg, azathioprine, corticosteroids greater than 20 mg per day [physiologic replacement doses are allowed], cyclosporine, mycophenolate, IVIG, interferon, sirolimus, sulfasalazine, tacrolimus).
- Immune modulators (eg, cytokines (eg, IL-2), granulocyte colony stimulating factor, growth hormone, tumor necrosis factor antagonists, thalidomide).
- Antineoplastic agents (except for topical agents for skin cancer).
- Prebiotics and probiotics other than the study medication.

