#### 3.0 STUDY DESIGN

A5350 is a phase II, randomized, double-blind, two-arm study that will enroll 90 HIV-infected participants ≥18 years of age, who have been on stable ART for at least 24 weeks prior to study entry, and have a CD4+ T-cell count >200 cells/mm³ prior to study entry and plasma HIV-1 RNA <50 copies/mL for 48 weeks prior to study entry. One blip ≤500 copies/mL within 48 weeks prior to study entry is allowed providing the preceding

and subsequent determinations are below 50 copies/mL. Randomization will be stratified by intent and eligibility to enroll in the substudy A5352s.

The primary objective of the study is to assess 24-week changes in sCD14 in participants treated with Visbiome Extra Strength compared to placebo.

A total of 90 participants will be randomized at 1:1 ratio to either Arm A (Visbiome Extra Strength + stable ART; treatment arm) or Arm B (placebo for Visbiome Extra Strength + stable ART; control arm). Participants will be on study for a total of 38 weeks. Probiotic Visbiome Extra Strength or placebo will be administered for 24 weeks after initiation at week 2. Participants will be followed for an additional 12 weeks after completing probiotic Visbiome Extra Strength treatment or placebo to determine whether the restoration to pre-intervention levels of gut microbial translocation products after discontinuation of the probiotics is associated with corresponding increases in levels of markers of immune activation, inflammation, and coagulation. Blood samples will be collected per the Schedule of Events (SOE) to measure markers of cellular activation, inflammation, and microbial translocation. Safety assessments will be performed per the SOE.

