    - NOTE: Participants who initiate ART within 6 months of HIV seroconversion are considered to have been initiated during acute infection and are excluded.
  - 4.2.2 Receipt of antibiotic therapy within 60 days prior to study entry.
    - NOTE: Antibiotics for OI prophylaxis are exclusionary.
  - 4.2.3 Known allergy/sensitivity or any hypersensitivity to components of Visbiome Extra Strength or its formulation.
  - 4.2.4 Use of investigational therapies or investigational vaccines within 90 days prior to study entry.
  - 4.2.5 Non-investigational vaccinations within 2 weeks prior to study entry.
  - 4.2.6 Active drug or alcohol use or dependence that in the opinion of the site investigator would interfere with adherence to study requirements.

- 4.2.7 Serious illness requiring systemic treatment and/or hospitalization within 30 days prior to entry.
- 4.2.8 History of positive HCV antibody with detectable HCV RNA in plasma within 48 weeks prior to study entry.

NOTE: Persons with positive HCV Ab but negative plasma HCV RNA are allowed to participate. Sites must document negative HCV RNA within 24 weeks of study entry.

- 4.2.9 History of positive HBsAg within 48 weeks prior to study entry.
- 4.2.10 Liver cirrhosis, history of inflammatory bowel disease, total colectomy, colon or rectal anastomosis, bowel resection, or current colostomy.
- 4.2.11 Current diagnosis of diabetes.
- 4.2.12 Either breastfeeding or pregnant within 24 weeks prior to study entry.
- 4.2.13 Ols within 45 days prior to study entry.
- 4.2.14 Use of any of the following medications/products for more than 3 consecutive days within the 60 days prior to study entry:
  - Immunosuppressives (eg, azathioprine, corticosteroids greater than 20 mg per day [physiologic replacement doses are allowed], cyclosporine, mycophenolate, intravenous immunoglobulin (IVIG), interferon, sirolimus, sulfasalazine, tacrolimus).
  - Immune modulators (eg, cytokines [eg, IL-2], granulocyte colony stimulating factor, growth hormone, tumor necrosis factor antagonists, thalidomide).
  - Antineoplastic agents (except for topical agents for skin cancer).
  - · Probiotics and prebiotics (supplements and products).

NOTE: Yogurt with live cultures is allowed.

- 4.2.15 History of lactose intolerance or milk allergy.
- 4.2.16 Any episode of acute or persistent diarrhea within 60 days prior to study entry.

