#### 5.1.3 Duration

Study treatment for Arm A participants is Visbiome Extra Strength, starting at week 2, for 24 weeks, followed by 12 weeks off study treatment. Study treatment for Arm B participants is placebo for Visbiome Extra Strength, starting at week 2, for 24 weeks, followed by 12 weeks off study treatment. All participants will be followed for 38 weeks after enrollment.

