#### Premature Treatment Discontinuation Evaluations

Participants who prematurely permanently discontinue study treatment will be followed on study/off study treatment per the SOE.

Site personnel should notify the protocol core team via e-mail ([contact]) within 48 hours of any participant who prematurely discontinues study product.

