4.3 Analysis Visit Windows

For all analyses, the following visit windows will be used:

- Screening: evaluations completed within 45 days of randomization.
- Entry (week 0): entry evaluations must occur on/after randomization and at least 24 hours after screening.
- Week 2: pre-treatment evaluation scheduled within a week [1, 3] window but prior to treatment initiation, treatment must begin within the next 72 hours after evaluation.
- On-treatment evaluations:
 - Week 4: weeks (3, 5]
 - Week 6: weeks (5, 8]
 - Week 14: weeks [12, 16]
 - Week 25 & 26: weeks [23, 28]
- Week 38: post-treatment evaluation scheduled within a week [36, 40] window.

If multiple results are available within the Week 6 or 14 visit windows the result closest to the scheduled visit will be used. If multiple results are available within the Week 38 window the result closest to 12 weeks after the last dose of study treatment (corresponding to protocol-defined 12 week washout) will be used.

Results within the weeks [23, 28] visit window will use the following logic to determine Week 25 and Week 26 results:

- If two results are collected on treatment the earlier will be Week 25 and the latter Week 26.
- If two results are collected off treatment the earlier will be Week 25 and the latter Week 26.
- If one result is collected on treatment and one result is collected off treatment the on treatment will be Week 25 and the off treatment Week 26.
- If only one result is collected it will be Week 25.
- If three or more results are available priority will be given to those collected on treatment and assigned Weeks based on the above rules.

For markers run in duplicate at entry and Week 2 and also at Weeks 25 and 26, "baseline" will refer to the average of entry and Week 2 and "Week 25/26" will refer to the average of Week 25 and Week 26. If only one result is available at either of these time points the single result will be used. For per-protocol analyses the "Week 25/26" calculation will only use results collected while on treatment.

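### The ban on non-study prebiotics and probiotics lapses at week 26, although weeks 26 to 38 are used to judge persistence off probiotics

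*Protocol*

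**What the plan says.** Protocol 5.4.2 introduces its list with "The following medications/products are prohibited while participants are taking the study agents". The last entry is "Prebiotics and probiotics other than the study medication". Under 5.1.3 each arm receives its product "starting at week 2, for 24 weeks, followed by 12 weeks off study treatment", and the table in 5.1.1 shows both arms off product from week 26 to week 38. For early stops, 6.2.4 states: "Participants who prematurely permanently discontinue study treatment will be followed on study/off study treatment per the SOE".

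Nothing else in the supplied documents extends the ban. Exclusion criterion 4.2.14, which covers probiotics and prebiotics and allows live-culture yogurt, only looks back: "Use of any of the following medications/products for more than 3 consecutive days within the 60 days prior to study entry". Substudy 5.1 refers to the main study's list, and the substudy ends at week 26. Clarification Memo 1 and Letter of Amendment 1 leave 5.4.2 alone.

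Protocol 3.0 gives the purpose of the last 12 weeks, and 9.1 repeats it in nearly the same terms: to learn whether the return of translocation products to earlier levels "after discontinuation of the probiotics is associated with corresponding increases in levels of markers of immune activation". SAP 4.3 picks, among several week 38 results, the one nearest to 12 weeks after the last dose, "corresponding to protocol-defined 12 week washout".

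The outcomes that depend on this period are gut microbiome diversity at week 38 (secondary outcome 9.2.2.8, hypothesis 1.2.8) and marker change from week 26 to week 38 (exploratory outcome 9.2.3.3, objective 1.6.5). Protocol 9.6.2 compares week 38 levels with baseline by linear regression. SAP 4.4 compares mean changes between arms in the per-protocol (PP) population.

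**The concern.** A period meant to show what happens after probiotics stop should not permit other probiotics. The protocol treats such use before entry as a reason for exclusion, and bans it on treatment. The SAP controls the timing of the week 38 specimen relative to the last dose. No rule controls exposure in between.

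Two readings of the week 38 data could suffer. If the study-product effect truly lasts, outside use in the placebo arm moves that arm towards Arm A and shrinks the difference. If the effect has gone, outside use in Arm A can leave week 38 values away from baseline, which looks like the persistence that hypothesis 1.2.8 predicts.

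**Working it through.** **Who is affected.** PP participants must stay on product to week 26 (SAP 4.1, criterion 2), so for them the ban ends exactly there. The primary PP sCD14 result uses only specimens up to week 25/26 taken on treatment (SAP 4.3), so later use cannot reach it. Participants who stop early lose the ban sooner, but they are outside PP. They enter the supplemental intent-to-treat analysis of Protocol 9.6, and possibly the fecal analyses, which SAP 3.2 assigns elsewhere.

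**The plan's own figures.** No stated figure bears directly on this point. The nearest is the precision table in Protocol 9.4: 36 evaluable per arm and a 95% CI of ±0.47 SD. Half-width = t(2n−2) × √(2/n) SD = 1.994 × √(2/36) = 0.470 SD. This reproduces. A two-sample t-test at 0.77 SD with 36 per arm has 89.6% power, matching the stated 90%. Both figures are for change to week 26; the protocol states no power for week 38.

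**Model for outside use.** All inputs here are assumptions, since the documents give neither uptake nor potency.

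- D: full effect of study product.
- c: true share of D still present at week 38.
- p: share of each arm using an outside product, 5%, 10% or 20%.
- k: effect of the outside product as a share of D, 0.25, 0.5 or 1.

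A user's week 38 effect is max(c, k)D in Arm A and kD in Arm B. A non-user's is cD and 0. Hence:

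- Arm A against baseline = D[(1−p)c + p·max(c, k)]
- Between arms = D[(1−p)c + p·max(c, k) − pk]

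With no carry-over (c = 0), the between-arm value is D(pk − pk) = 0, while Arm A appears to keep pkD. With full persistence (c = 1), the between-arm value is (1 − pk)D. Each cell shows the apparent Arm A effect at c = 0, then the between-arm difference at c = 1:

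| p | k = 0.25 | k = 0.5 | k = 1 |
|---|---|---|---|
| 5% | 0.0125D; 0.9875D | 0.025D; 0.975D | 0.05D; 0.95D |
| 10% | 0.025D; 0.975D | 0.05D; 0.95D | 0.10D; 0.90D |
| 20% | 0.05D; 0.95D | 0.10D; 0.90D | 0.20D; 0.80D |

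The error runs from about 1% to 20% of D, with 5% in the middle cell. The zero between arms rests on equal uptake. With c = 0 and unequal uptake it becomes k(pA − pB)D; for example, 10% against 5% at k = 0.5 gives 0.5 × 0.05 × D = 0.025D.

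**Would leaving users out help?** Omitting 5%, 10% or 20% of 36 leaves about 34, 32 or 29 per arm. The same formula gives half-widths of 0.484, 0.500 and 0.526 SD. For illustration only, take 0.77 SD as the week 38 difference with c = 1. Power after omission is 87.9%, 85.8% and 82.2%. Keeping users gives 88.9%, 88.1% and 86.4% at k = 0.25, then 88.1%, 86.4% and 82.6% at k = 0.5, and 86.4%, 82.6% and 73.2% at k = 1. Omission is worse in six of nine cells and better only at k = 1.

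**The case against.** The strongest reply is that this is a choice of scope. The dosing sections speak of being off study product and promise no abstinence from other probiotics; the washout label appears in an SAP parenthesis about choosing among results. Durability under ordinary behaviour is a legitimate target. But 3.0 and 9.1 describe the period as one after discontinuation of the probiotics, so this reply does not fit the protocol's stated purpose.

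The placebo arm is a real safeguard. With equal uptake, Arm B would show the same shift from baseline as Arm A when nothing carries over, which would expose false persistence. The risk then lies in reading Arm A alone, plus dilution of a true difference.

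A reader might infer that outside use would go unrecorded. The documents do not support that. Section 6.3.4 puts over-the-counter products and dietary supplements on the CRF with start and stop dates, 6.3.8 carries this past entry, and the schedule has dietary and clinical assessments at week 38. Probiotics are not named in 6.3.4, but the examples there are not exhaustive. Naming them would add detail and nothing more.

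A reader might also infer that the SAP wrongly omits a rule for week 38 diversity. That is not shown: the SAP marks this outcome as analysed elsewhere, and that plan was not supplied.

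**Conclusion.** The concern holds as a gap between the rule and the purpose of the period: 5.4.2 permits, from week 26, an exposure that the persistence assessment is meant to exclude. Its size cannot be derived from the documents. The range of about 1% to 20% of D restates assumed uptake times assumed potency. I expect a value near the low end, because 4.2.14 screens out recent users and the study product is a high-dose formulation, but that is judgement.

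Two stronger readings should be resisted. The gap does not threaten the primary week 26 sCD14 result. Participants who stop early are not a main route of bias either, since they fall outside the PP population that SAP 4.4 uses for continuous outcomes. This is an inexpensive improvement to secondary and exploratory outcomes.

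**What to change.** 1. In Protocol 5.4.2, extend the prebiotic and probiotic line through week 38, and carry over the live-culture yogurt allowance of 4.2.14. The other entries can stay tied to treatment.
2. In SAP 4.1, date criterion 3 through week 26, in line with criteria 2 and 4, and do the same for the matching criterion in Protocol 9.6. Without this, use in week 30 would count as prohibited once the ban is extended, and could remove a valid week 26 result.
3. Optional: a week 38 sensitivity analysis that omits specimens from recorded users, for example by the 4.2.14 rule of more than 3 consecutive days in the preceding 60. The planned analysis stays the main one. The sensitivity analysis conditions on behaviour after randomization and loses precision, as shown above.

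The cost is one protocol line, one date in the PP definition, and 12 more weeks of a minor restriction on participants. No visit falls between weeks 26 and 38, so compliance can be checked only at the week 38 visit. No new CRF field is needed.

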# 5.4.3 Precautionary Medications

Antibiotics. Some strains of bacteria in Visbiome Extra Strength may be inactivated by certain antibiotics. Do not consume the study products within 4 hours after taking antibiotics.

# 5.5 Unblinding

Unblinding of study products (Visbiome Extra Strength and the placebo for Visbiome Extra Strength) will occur in accordance with the ACTG Unblinding Subjects Standard Operating Procedure (SOP) 123, located at: https://member.actgnetwork.org/cms/dl/10466.

Individual requests for unblinding will be handled on a case-by-case basis by the A5350 team leadership. The site pharmacists are not to reveal unblinded treatment information. More information regarding the site pharmacist role is in the "Pharmacy Guidelines and Instructions for DAIDS Clinical Trials Networks."

# 6.0 CLINICAL AND LABORATORY EVALUATIONS

# 6.1 Schedule of Events

		Entry Week 0	Post-Entry								
Evaluation (Within 4) days prio	Screening		Week 2 ±7days	On Treatment Post Treat. (Weeks) (Weeks)					10.25	Conf. of	Prem.
	(Within 45 days prior to entry)			4	6	1 4	2 5	26	38	Virologic Failure	Study DC
	,,,,,,,,,,,,,,,,,,,,,,,,,,,,,,,,,,,,,,,		iruays		±7 days			±7 days			
Documentation of HIV	Х										
Medical History/ Medication History	Х		Х								
Targeted Physical Exam	Х		Х		Х	Х		Х	Х		Х
Height	Х		i i				-				
Weight	Х		2					Х	X		
Clinical Assessments			Х		Х	Х		Х	Х		х
Dietary Assessment		z	Х		Х	Х		Х	Х		
Sexual Activity Assessment			Х		Х	Х		Х	Х		
Bowel Symptom Assessment			Х		Х	,		Х			
Fatigue Symptom Assessment			Х			Ÿ		Х			
Dispense Study Products			Х			Х					
Hematology	Х		X			X		Х	X		
Liver Function Tests	Х		Х			Х		Х			7
Blood Chemistries	Х		Х			X		Х			
Calculated CrCl	Х										
Fasting Lipid Profile			Х			Х		Х			
Pregnancy Testing	Х	Х	·s		lf		nanc				
Hepatitis Serology	Х	5									
CD4+/CD8+	Х		Х			Х		Х	×		
Stored Plasma for sCD14		Х	Х		Х	Х	Х	Х	Х		Х

		-	8		F	Post-E	ntry				1.
Screening Evaluation (Within 45 days prior	Screening	Entry Week 0		On Treatment (Weeks)					Post Treat. (Weeks)	Conf. of	Prem.
			Week 2 ±7days	4	6	1 4	2 5	26	38	Virologic Failure	Study DC
			_rudy3			±7 da	iys		±7 days		
Stored Plasma for Soluble Markers of Inflammation, Coagulation, Immune Activation, and Gut Epithelial Barrier Integrity		х	×		X	х	х	X	х		
Stored Plasma for Insulin Resistance			Х		i i	Χ		Х			er e
Stored Plasma for Kynurenine to Tryptophan Ratio			х		8			х			
Stored peripheral blood mononuclear cells (PBMCs) for Monocyte and T- cell Phenotyping			x			x		х	x		
Stored Plasma for Enterocyte Death (I-FABP)			х		X	X	X	Х	X		
Stored PBMC for Future Analysis			Х		Х	Х		Х	Х		
Stored Plasma for Future Analysis			Х		Х	Х	5	Х	Х		
Plasma HIV-1 RNA	Х		Х			X		Х		Х	х
Fecal Sample and Rectal Swabs			Х		Х	Χ		Х	Х		
Telephone Assessment				Х							
Adherence Assessment					X	X		Х			Х
Empty Sachet Count					Х	Х		Х			Х

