# Stored Plasma for Soluble Markers of Inflammation, Coagulation, Immune Activation, and Gut Epithelial Barrier Integrity

Plasma specimens for measurement of IL-6, IP10, sCD163, TNF-RI, D-dimer, LPS, LBP, and oxidized LDL will be collected and stored for batch analysis at the end of the study. For storage and shipping, please see the A5350 LPC.

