#### Enterocyte Death Assessment

Plasma specimens for measurement of I-FABP will be collected and stored for batch analysis at the end of the study. For storage and shipping, please see the A5350 LPC.

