#### 9.2.2 Secondary Outcome Measures

- 9.2.2.1 Change from baseline to week 26 in systemic inflammation markers (IL-6, IP10, sCD163, TNF-RI, oxidized LDL), kynurenine to tryptophan (KT) ratio, and coagulation marker (D-dimer).
- 9.2.2.2 Change from baseline to week 26 in microbial translocation markers (LPS, LBP).
- 9.2.2.3 Change from baseline to week 26 in CD4+ lymphocyte counts and CD4+/CD8+ ratio.
- 9.2.2.4 Change from baseline to week 26 in markers of monocyte and lymphocyte activation and senescence.
- 9.2.2.5 Change from baseline to week 26 in gastrointestinal microbial diversity from fecal samples.
- 9.2.2.6 Change from baseline to week 26 in enterocyte death (I-FABP).
- 9.2.2.7 Occurrence of Grade ≥3 AEs related to study product.
- 9.2.2.8 Diversity of gut microbiome at week 38.

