# 9.6 Analyses

All statistical tests will be two-sided with a nominal alpha level of 0.05. Because this is a phase II study and all potential biologic activities of the intervention are of interest, analyses will be as-treated, and limited to participants who 1) have baseline and week 26 sCD14 measurements, 2) remain on study product through week 26 (participants with more than 50% on average of missed study product may be excluded), 3) have not used prohibited medications, 4) do not have a confirmed virologic failure (as defined per section 6.2.3 at or prior to week 26, and 5) do not experience inflammatory conditions, receive vaccines, or have concurrent illness (as defined per section 6.2.3).

NOTE: Participants experiencing inflammatory conditions at the time of a visit are instructed to wait 7 days before measurements are obtained. Measurements obtained while inflammatory conditions are present will not be included in the analysis. A supplemental intent-to-treat analysis will also be performed and will include all randomized participants. No adjustment for multiple testing will be performed. A summary of the number of participants experiencing study product-related AEs and the types of AEs will be reported, as will the proportion of participants who discontinue study product after entry.

To reduce intra-participant variability, two blood draws will be performed at baseline (entry and week 2) and week 26 (week 25 and week 26) and the measurements will be the average of two for sCD14. If repeat measurements are not available at either of these time points, a single measurement will be used rather than the average.

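### I-FABP has one baseline draw but two end-of-treatment draws, which costs precision on a secondary outcome and leaves its averaging rule unstated

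*Protocol*

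**What the plan says.** Protocol section 6.1 gives plasma for I-FABP its own row, "Stored Plasma for Enterocyte Death (I-FABP". It is marked at weeks 2, 6, 14, 25, 26 and 38, and the entry cell is blank. Two neighbouring rows, "Stored Plasma for sCD14" and "Stored Plasma for Soluble Markers of Inflammation, Coagulation, Immune Activation, and Gut Epithelial Barrier Integrity", are marked at entry and week 2 and again at weeks 25 and 26. Neither Clarification Memo #1 nor Letter of Amendment #1 changes the I-FABP row.

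The contents of the soluble-marker row are spelled out in section 6.3.15: "Plasma specimens for measurement of IL-6, IP10, sCD163, TNF-RI, D-dimer, LPS, LBP, and oxidized LDL will be collected and stored". I-FABP is not on that list. It has a separate entry, which names no visits: "Plasma specimens for measurement of I-FABP will be collected and stored for batch analysis at the end of the study".

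The outcome is listed in its own right at 9.2.2.6: "Change from baseline to week 26 in enterocyte death (I-FABP". SAP section 3.2 repeats it.

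Protocol section 9.6 gives the purpose of the paired draws: "To reduce intra-participant variability, two blood draws will be performed at baseline (entry and week 2) and week 26 (week 25 and week 26". It then names averaging for sCD14 only. SAP section 4.3 extends averaging to other markers, but on a condition: "For markers run in duplicate at entry and Week 2 and also at Weeks 25 and 26". It adds that where only one result exists at a time point, that result is used.

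**The concern.** Week 25 is marked for only three rows in the schedule: sCD14, the soluble-marker panel and I-FABP. A week 25 draw for I-FABP makes sense as half of a pair, yet the matching entry draw is missing and neither document says why. Half of the noise reduction available from paired draws is therefore not obtained for this marker.

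There is also a gap in definition. I-FABP does not meet the SAP's condition for averaging, because it is not duplicated at baseline. One analyst could use week 2 against the average of weeks 25 and 26. Another could follow the outcome's wording and use week 26 alone.

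Finally, a duplicated marker can fall back on the other baseline draw if one specimen is lost. I-FABP cannot: a lost week 2 sample removes that participant's change score.

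**Working it through.** **Inputs.** Draws per end come from protocol 6.1: I-FABP 1 at baseline and 2 at the end (1+2); sCD14 and the soluble-marker panel 2+2. Evaluable participants for secondary endpoints are 36 per arm (protocol 9.4), with two-sided alpha 0.05 (9.6). The documents give neither the SD of I-FABP change nor its within-person share, so a range is assumed below.

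**Step 1: the plan's own table.** For 36 against 36, a two-sample t-test (70 df) gives power of 89.6%, 80.1% and 69.5% at 0.77, 0.67 and 0.59 SD. The 95% CI half-width is t(0.975, 70) × sqrt(2/36) = 0.470 SD. These match the stated 90%, 80%, 70% and ±0.47 SD. The table is in SD units, so it is not wrong. The sampling scheme acts through the size of the SD itself.

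**Step 2: variance of the change score.** Let w be the within-person variance of one draw and T the between-person variance of true change. With independent draws,

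Var(change) = T + w × (1/m_baseline + 1/m_end).

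The within-person part is:
- 1+1 draws: w × (1 + 1) = 2.0w
- 1+2 draws (I-FABP as scheduled): w × (1 + 1/2) = 1.5w
- 2+2 draws (entry added): w × (1/2 + 1/2) = 1.0w

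The scheduled design obtains half of the possible reduction from 2.0w to 1.0w.

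**Step 3: effect on SD, sample size and power.** T/w is unknown and is varied from 0 to 2. The variance ratio is (T/w + 1.5)/(T/w + 1.0). The SD reduction from adding entry is 1 − sqrt(1/ratio). The number per arm needed under 1+2 to match 2+2 is 36 × ratio. Power is for 1+2 at 36 per arm, for an effect of 0.77 SD of the 2+2 change (89.6% power under 2+2).

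| T/w | Variance ratio | SD reduction from adding entry | Per arm to match | Power under 1+2 |
|---|---|---|---|---|
| 0 | 1.5/1.0 = 1.50 | 18% | 54 | 75% |
| 0.5 | 2.0/1.5 = 1.33 | 13% | 48 | 80% |
| 1 | 2.5/2.0 = 1.25 | 11% | 45 | 82% |
| 2 | 3.5/3.0 = 1.17 | 7% | 42 | 85% |

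**Step 4: can the protocol's sCD14 data narrow the range?** Protocol 9.4 cites SDs of change of 0.11 (single) and 0.06 (average of two) from 20 placebo participants. In the model, w = 0.11² − 0.06² = 0.0121 − 0.0036 = 0.0085, and T = 0.0036 − 0.0085 = −0.0049, which is impossible. These figures show that duplication can matter for a plasma marker in this population. They cannot calibrate the gain for I-FABP.

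**The case against.** - **The protocol promises averaging only for sCD14.** This is true. Other plasma measures, such as the KT ratio and insulin resistance, are single draws at both ends. The point is therefore a design improvement and a missing SAP sentence, not a departure from the plan. The comparison is with sCD14 and the listed soluble-marker panel, not with every marker in the trial.
- **A reader might infer that the week 25 draw is wasted,** because I-FABP fails the SAP's condition for averaging. The documents do not support that. The single-result rule in SAP 4.3 leads naturally to week 2 as baseline against the week 25/26 average. The same section makes a lone result in the window the week 25 value, and limits per-protocol values to those taken on treatment, so the extra draw is also a back-up.
- **A reader might infer a gain equal to doubling the sample.** That needs 2.0w as the starting point, hence the strictest reading of one sentence, and also no variation in true change. The step from 2.0w to 1.5w needs only an SAP sentence, so it cannot be credited to the entry assay. Even the 50% figure is a ceiling, reached at T = 0.
- **Independence is doubtful.** Protocol 6.2.3 lets week 26 follow week 25 by as little as 24 hours. Correlated end draws raise the variance under both schemes and shrink the relative gain. This stands as a caveat.
- **Entry plasma may not be spare.** It is designated for other assays, and plasma for future analysis is not marked at entry. This stands: availability must be confirmed.
- **The core fact is one blank cell in a dense table.** Neighbouring rows keep their entry marks, so a lost mark is unlikely, but the cell should be checked against the source document.

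**Conclusion.** The point holds as a modest loss of precision on one secondary outcome, together with an undefined averaging rule. As scheduled, the within-person part of the I-FABP change variance is 1.5 units where 1.0 was attainable. With independent draws and true-change variance of 0 to 2 times the within-person variance, adding entry would lower the SD of change by about 18% down to 7%. This equals about 50% down to 17% more evaluable participants for this marker (54 down to 42 per arm, against 36). The range rests on assumed variance components, because the documents give none for I-FABP.

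Both arms are sampled alike, so the comparison is not biased. The sCD14 analysis and the stated power table are unaffected. The priority is low, but the remedy is cheap.

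**What to change.** 1. Assay I-FABP on entry plasma as well, after confirming spare aliquot volume, or mark I-FABP at entry in the Schedule of Events. Then treat it as a duplicate marker in SAP 4.3.
2. Whether or not that is done, add a sentence to SAP 4.3: the I-FABP week 25/26 value is the average of both draws (on-treatment draws only in per-protocol analyses), even if its baseline is the single week 2 value.

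The first change costs about 90 more assays (one per randomized participant, 45 + 45), run in the planned end-of-study batch, and uses some entry plasma. Using plasma already stored needs no added visit. The second change costs one sentence.
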